	For the primary efficacy analysis, subjects who provide modified Ashworth and CGIC scores at Visit 11 and meet the treatment failure criterion at Visit 11, or who have met the treatment failure criterion at any prior visit will be classified as being treatment failures. All other subjects will be classified as not being treatment failures.
Secondary Efficacy Outcomes:	Subject Global Impression of Severity (SGIS)
Safety Assessments:	
 
Treatment Emergent Adverse Events
 
Daytime sedation
 
Vital Signs (seated blood pressure and pulse)
 
Clinical laboratory tests
 
12 Lead ECG
 
Physical examination and neurological evaluation
 
Columbia – Suicide Severity Rating Scale
 

Treatments:	•
Study Population:	Subjects aged 18 years and above with spasticity due to multiple sclerosis with acceptable symptom control
Number of Subjects:	Approximately 300 subjects will be enrolled to ensure that at least 240 subjects are randomized at the beginning of
Number of Centers:	Up to 35 centers
Setting:	Out-patient clinics
Statistical Methods:	Efficacy Analyses: The primary efficacy analysis will be performed on an intent-to-treat (ITT) population, defined as all subjects who were randomized to double-blind study drug at Visit 7 and subsequently received at least one dose of study medication.
	).
	A per protocol (PP) population may also be analyzed (if it differs from the ITT population overall by more than 10% in sample size), defined as all ITT population subjects who had at least one on-treatment assessment in Part 3, and did not have any major protocol violation (such as poor compliance).

Confidential Page 3 of 67

Confidential Page 4 of 67

used medications.

Subject listings will be provided for all safety parameters as well as recently and concurrently

Table 1: STUDY DESIGN AND SCHEDULE OF ASSESSMENTS

		1 a	DIC 1. 510	DESIGN I	ALID SCHED	ULE OF ASS	ESSIVIE VIS					
Visit	S	Run- In		Open-La	abel				Double-		bo-Controlle ation	d Down-
	Screening											
	(-14 days)	Visit 1	Visit 2	Visit 3	Visit 4	Visit 5	Visit 6	Visit 7	Visit 8	Visit 9	Visit 10	Visit 11
Week												
Informed consent	×		_			_						
Demographics	×											
Medical and medication	×	×										
history												
Physical examination 	×											× 
Neurological examination	×											× 
Vital sign measurements 	×	×	×	×	×	×	×	×	×	×	×	×
		x										

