## 3.1.3 Exoploratory Objectives

#### 3.2 Study Design

The study is a multicenter, out-patient trial in subjects with spasticity due to MS (Multiple Sclerosis). The study will be performed in three parts: a 1-week open-label phase (Part 1)

week open-label phase (Part 2)

a 16-

and a 4-week, double-blind, placebo-controlled, randomized withdrawal phase (Part 3). Subjects will be informed that at some time during the study, they may receive placebo, however, they will not be informed at which visit this will commence. An overview scheme of the study and the schedule of events are presented in Section 3.2.3.

Approximately 300 subjects will be enrolled to ensure that at least 240 subjects are randomized in Part 3. Subjects will be screened for eligibility within 14 days of the initial visit by medical history, recent and concomitant medication use, physical and neurological examination, 12-lead ECG, clinical laboratory testing, and assigned a subject number. Following provision of informed consent and successful screening, eligible

Version 9.0

subjects will be enrolled in the study (Vis	it 1). Once on study, subjects will be seen in the
clinic at the end of the 7-day	(Visit 2), at which point they will be
converted to	. They will be seen in the clinic every 2 weeks
	_

subjects are to remain on a fixed dose for an additional 12 weeks;

At the beginning of Week 18 (Visit 7), subjects who have remained on a fixed dose of for 12 to 16 weeks, without further need for adjustment in medication, will be randomly assigned to either remain on in the same dose or placebo for an additional 4 weeks.

The final scheduled study visit is Visit 11,

Subjects will be evaluated for efficacy as briefly described below. The efficacy instruments and assessments are further described in Section 6.2.

Right and left hip flexion and abduction, knee flexion and extension, and ankle dorsiflexion and plantar flexion will be assessed using the modified

Ashworth Scale, 6-point version (inclusive of 1+), rated from 0 to 4, for a total of 12 movements being evaluated. This same individual will query the subject for any changes in physiotherapy regimen. The modified Ashworth Scale assessment is further discussed in Section 6.2.1.

• Clinician Global Impression of Change (CGIC) will be assessed by the Treating Physician,

The Subject Global Impression of Severity (SGIS) will be assessed at Visits 4, 7, 8, 9, 10, and 11.

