## 3.2.1 Sample Size Considerations

3.2.2 Randomization

treatment

Approximately 300 subjects will be enrolled to ensure that at least 240 subjects are randomized at the beginning of Week 14 (Visit 7).

Subjects who finish Visit 7 (at the beginning of Week 18) will be randomized to double-blind

Page 14 of 53

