#### **Intent-to-Treat (ITT) Population:**

The ITT population will be defined as all subjects who are randomized to double-blind study drug at Visit 7 and subsequently received at least one dose of study medication, and have one subsequent modified Ashworth and CGIC score at the same assement.

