#### Per Protocol (PP) Population:

The per protocol (PP) population will be defined as all subjects who are randomized to double- blind study drug at Visit 7, subsequently receive at least one dose of study medication, have at least one subsequent modified Ashworth and CGIC score at the same assement, and do not have any important protocol deviations. Protocol deviations will be reviewed and subjects with important/not important violations will be identified prior to unblinding the clinical database.

In addition, concomitant medications will be reviewed for anti-spasticity medication use, its dose, and the timing relative to the in-clinic assessment. Adverse events will be reviewed in a similar fashion for confounding medical conditions. Finally, confounding due to changes in physiotherapy regimen will be assessed. In-clinic Ashworth assessments that are judged to be potentially confounded will be flagged. The analysis of the PP population will exclude such potentially confounded assessments.

Analyses of the primary efficacy endpoint will be repeated using the PP population if it differs in size from the ITT population in total number by more than 10% overall.

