### 6.1 Study Subjects

### 6.1.1 Subject Disposition

The final study disposition of each subject will be captured in the eCRF. For those subjects who do not complete the study as planned, all potential reasons for discontinuation should be provided, with one indicated as primary. The reasons for discontinuation will be categorized as described below and the following descriptive summaries of study disposition will be provided.

- Number of subjects who were enrolled in each phase of the study (Part 1, Part 2, Part 3):
  - o Part 1: Received at Visit 1
  - o Part 2: Received at Visit 2 (Safety Population)
  - o Part 3:
    - Randomized at Visit 7
    - Dispensed Blinded Study Drug at Visit 7 (Safety Population Part 3) by treatment group and overall
    - Intent-to-Treat Population by treatment group and overall
    - Per Protocol Population by treatment group and overall
- Number and proportion of subjects (overall for Parts 1 and 2 and by treatment group and overall for Part 3) who discontinued each phase of the study.
- Number and proportion of subjects (overall for Parts 1 and 2 and by treatment group and overall for Part3) who dropped-out for each of the following categories (based on primary reason and also based on all reasons) for why a subject may be prematurely discontinued from the study.

- Withdrew Consent
- Adverse Event
- MS-related Disease Progression

0

- Required Dose Change Between Visit 4 and Visit 11
- Major Protocol Deviation
- Lost to Follow-up
- Worsening of Clinical Condition or Loss of Efficacy
- o Withdrew, Per Sponsor
- o Withdrew, Per Investigator
- Other

A listing of subject disposition will be prepared, inclusive of dates of last dose and last contact, and any investigator comments regarding reason for discontinuation. A summary table will tabulate overall disposition of the subjects by the categories above. A CONSORT figure will summarize subject disposition.

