### 6.2.1.6 Sensitivity Analysis of the Primary Efficacy Analysis

Several sensitivity analyses of the impact of missing data on the primary efficacy endpoint will be performed. First, the primary efficacy analysis will be repeated in the PP population if it differs in size from the ITT population by more than 10% overall. In addition, the primary efficacy analysis will also be performed (using the ITT population) with different assumptions regarding the response status of a subject with missing data.

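### The per-protocol repeat of the primary analysis depends on a headcount pooled over arms, so it can be left out when exclusions or flagged Ashworth ratings fall mainly in one arm

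*SAP*

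**What the plan says.** The primary analysis compares failure rates between two arms in the ITT population. Subjects either stay on active treatment "in the same dose or placebo for an additional 4 weeks".

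Under SAP 5.1, ITT subjects must be randomized, dosed, and "have one subsequent modified Ashworth and CGIC score at the same assement". PP carries a similar rating requirement, so what separates the two populations is essentially the removal of subjects with important protocol deviations. The PP analysis also leaves out in-clinic Ashworth assessments flagged as potentially confounded by anti-spasticity medication, adverse events or changes in physiotherapy.

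Whether this analysis is run depends on size:

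- SAP 5.1 repeats the primary endpoint analysis in PP "if it differs in size from the ITT population in total number by more than 10% overall".
- SAP 6.2.1.6 puts it first among the sensitivity analyses: "the primary efficacy analysis will be repeated in the PP population if it differs in size from the ITT population by more than 10% overall".
- Protocol 10.3.1.2 has the same rule. The protocol synopsis has the same threshold but says only that PP may be analyzed, "if it differs from the ITT population overall by more than 10% in sample size".
- SAP 6.1.2 applies the 10% rule to the PP demographic summaries.

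No by-arm condition appears in the readable text. SAP 6.1.1 does report "Per Protocol Population by treatment group and overall" in the disposition summary, and SAP 6.1.3 summarizes Part 3 violations by treatment group. PP membership is settled before unblinding (SAP 5.1, 5.5, 5.6).

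**The concern.** A comparison of two failure rates is disturbed by who is excluded from each arm and by how those subjects fared. A pooled count carries neither piece of information.

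Uneven exclusion is plausible in a randomized-withdrawal design. SAP 6.1.3 counts as important deviations the use of excluded concomitant medication and the development of withdrawal criteria without withdrawal. Protocol 5.3 lists intolerable spasticity among the justifiable reasons for removal. Subjects who lose active drug may meet these conditions more often, although the documents give no deviation rate and no split.

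The flagged assessments raise a second gap. The trigger counts subjects, whereas the flags remove assessments. Many flags in one arm could leave the headcount unchanged, and the analysis designed to handle them would then not be required.

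What is at stake is a planned check on whether the failure-rate difference depends on deviating subjects or confounded ratings. The ITT test is not at stake.

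**Working it through.** **Inputs.** The threshold is more than 10% of the total (SAP 5.1). On size, the SAP plans enrolment so that "at least 240 subjects are randomized". I take 240 in ITT. There are two arms (SAP 3.2). The allocation ratio is not readable, so I assume 1:1 and show other ratios. The failure rates below are illustrative, since the readable text gives none.

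**Step 1: where the rule switches.** It fires when (N_ITT − N_PP) / N_ITT > 0.10.

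- 24/240 = 10.0%, which is not more than 10%, so PP is not required.
- 25/240 = 10.4%, so PP is required.

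**Step 2: how the same total can be split** (120 per arm; Fisher exact test of the imbalance).

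| Excluded, arm A v arm B | Share of each arm | Pooled | PP required? | Fisher p |
|---|---|---|---|---|
| 24 v 0 | 20.0% v 0% | 10.0% | No | about 3e-8 |
| 20 v 4 | 16.7% v 3.3% | 10.0% | No | 0.0009 |
| 12 v 12 | 10.0% v 10.0% | 10.0% | No | 1.0 |
| 13 v 13 | 10.8% v 10.8% | 10.8% | Yes | 1.0 |

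**Step 3: other allocation ratios.** The largest one-arm share that does not trigger the rule is 24 divided by the size of that arm.

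| Ratio | Arms | Larger arm | Smaller arm |
|---|---|---|---|
| 1:1 | 120, 120 | 20.0% | 20.0% |
| 3:2 | 144, 96 | 16.7% | 25.0% |
| 2:1 | 160, 80 | 15.0% | 30.0% |
| 3:1 | 180, 60 | 13.3% | 40.0% |

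At 1:1 the limit was also checked for ITT sizes of 200, 220, 228 and 260, and stays between 19.3% and 20%.

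**Step 4: what might go unseen.** Take ITT failures of 48/120 (40%) on placebo and 24/120 (20%) on active. The difference is 20 points (pooled z-test p = 0.0007). Remove 24 placebo subjects, of whom f failed. The PP placebo rate is (48 − f)/96, and the active rate stays at 20%.

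| f of 24 | PP placebo rate | PP difference | p |
|---|---|---|---|
| 0 | 48/96 = 50.0% | 30.0 points | 0.000003 |
| 6 | 42/96 = 43.8% | 23.8 points | 0.0002 |
| 10 | 38/96 = 39.6% | 19.6 points | 0.002 |
| 18 | 30/96 = 31.3% | 11.3 points | 0.058 |
| 24 | 24/96 = 25.0% | 5.0 points | 0.38 |

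The headcount is the same in every row, so the rule gives the same answer, not required, in all five.

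**Step 5: flagged assessments.** If a subject keeps PP status while one or more Ashworth ratings are dropped, N_PP does not change. The left side of the rule in step 1 is then unaffected however many ratings are flagged, or in which arm.

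**The case against.** The case on the other side has force in several places.

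- **Low consequence.** PP is a sensitivity analysis and the primary test is ITT. Under one-sided exclusion PP is itself open to selection, so it is hardest to interpret where it is most wanted. This stands, and it is why the point is minor.
- **Partly covered elsewhere.** PP counts and Part 3 violations appear by arm. Listings 16.2.3.3 and 16.2.6.1 give analysis-set membership and treatment failure by subject. Protocol 10.4.3.4.2 plans exploratory subgroups by neurological concomitant medication. SAP 5.6 allows further exploratory analyses, so PP is not forbidden below the threshold. All true, but by-arm counts do not show the effect on failure rates. Rebuilding the result from listings is not a planned analysis, and it is harder still for the flagged ratings.
- **Other sensitivity analyses exist.** SAP 6.2.1.6 also plans ITT re-analyses under different assumptions about missing response status, and the readable text attaches no size condition to them. Protocol 10.4.3.2.1 lists items (a) to (d), which are blacked out. One cannot say that PP is the only robustness check. In the readable text it is the only primary-endpoint analysis that deals with both deviations and flagged ratings.
- **24 against 0 is constructed.** It is a boundary case, not a forecast. Eligibility violations arise before randomization and have no evident reason to be one-sided.

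A reader might also infer that the rule is faulty because it fires on balanced exclusions such as 13 v 13. That is not a defect: an extra supportive analysis does no harm, and equal counts can still differ in reason and outcome.

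**Conclusion.** The concern holds as a minor point. The size condition does not measure what could disturb the between-arm comparison, and it can leave the PP analysis out when exclusions or flagged ratings are concentrated in one arm. With 240 in ITT and an assumed 1:1 split, up to 20% of one arm and none of the other can be excluded without triggering it. That figure is not fixed: at 3:2 to 3:1 it is about 13% to 40%, depending on the ratio and the arm.

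It is tempting to conclude that the omitted analysis would weaken the trial's result. The documents do not support that. In the illustration the PP difference runs from 5 to 30 points around an ITT difference of 20. Excluded medication could mask worsening on placebo, which would enlarge the PP difference. The direction is unknown, and the ITT test is unaffected whichever way it goes.

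**What to change.** Delete the 10% condition in SAP 5.1 and 6.2.1.6, and in 6.1.2 for the PP demographics, and state that the primary analysis will always be repeated in the PP population. Show the number excluded and the number of flagged Ashworth assessments beside the result, by arm and by reason. SAP section 2 says that the SAP prevails over the protocol's statistical section, so the change can be made there.

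A by-arm trigger should not be used instead. Populations are settled while blinded, when only the pooled count is known, so such a rule could be evaluated only after treatment is revealed. A limit of 10% in either arm would catch 24 v 0, but it would still ignore flagged ratings that leave the headcount unchanged.

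The cost is a wording change and a PP counterpart to Table 14.2.1, if the blacked-out part of the table list does not already hold one. The downside is one more supportive result that is open to selection when exclusions are one-sided. It must be labelled a sensitivity analysis only.

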#### 5.2 P-Values

Unless stated otherwise, all significance tests will be two-sided with statistical significance (alpha,  $\alpha$ ) assessed at the 5% level. All p-values will be reported to four decimal places. P-values will not be adjusted to account for multiple comparisons.

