#### 10.6 Level of Significance

All statistical tests will be carried out at the alpha=0.05 level of significance.

Confidential Page 62 of 67

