#### 4. STUDY ENDPOINTS AND DEFINITIONS

## 4.1 Primary Efficacy Endpoint

The primary efficacy variable is the proportion of subjects who become a treatment failure during the double-blind randomized withdrawal part (Part 3). A subject's response status will be determined after database lock, but prior to unblinding the data. A subject who meets the following criterion will be considered a treatment failure:

• A CGIC of  $\geq$  5 ("minimally worse" to "very much worse") and at least one movement with a  $\geq$  1 unit increase 1 in modified Ashworth score from Baseline

Derivation of the primary endpoint is outlined in Section 6.2.1.3.

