### 4.2 Secondary Efficacy Endpoints

• The secondary efficacy variable is the difference between treatment groups in Subject Global Impression of Severity (SGIS) scores at Visit 11. If Visit 11 is missing, the last available SGIS will be used.

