### **5.4 Interim Analysis**

An interim analysis will not be performed.

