### 6.2.1.5 Primary Efficacy Analysis

The primary efficacy analysis will be performed using the intent-to-treat (ITT) population.

The primary efficacy analysis will be carried out using a two-sided test at the alpha=0.05 level of significance.

. Alternate approaches to handling missing data are discussed in Section 6.2.1.6.

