#### 6.2.2.2 Secondary Analysis of SGIS

If Visit 11 is missing, the last available SGIS will be used.

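### No readable text makes the SGIS test depend on the primary result; the SAP should state the order of testing, or refer to it in section 5.2 if it is already set elsewhere

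*SAP*

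**What the plan says.** **Level.** SAP 5.2 sets the default: "Unless stated otherwise, all significance tests will be two-sided with statistical significance" judged at 5%. For the primary, SAP 6.2.1.5 repeats it: "The primary efficacy analysis will be carried out using a two-sided test at the alpha=0.05 level of significance". Protocol 10.6 is equally general: "All statistical tests will be carried out at the alpha=0.05 level of significance".

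**Multiplicity.** SAP 5.2 continues: "P-values will not be adjusted to account for multiple comparisons".

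**Endpoints.** SAP 4.1 names one primary: "The primary efficacy variable is the proportion of subjects who become a treatment failure during" Part 3. SAP 4.2 names one secondary: "The secondary efficacy variable is the difference between treatment groups in Subject Global Impression of Severity (SGIS) scores at Visit 11".

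**SGIS analysis.** In SAP 6.2.2.2 only the missing-visit rule can be read: "If Visit 11 is missing, the last available SGIS will be used". The test, its level and any condition on the primary are not visible there.

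**Interim looks.** SAP 5.4: "An interim analysis will not be performed". No alpha is spent elsewhere in that way.

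**The concern.** Under the readable rules, an SGIS p-value below 0.05 counts as statistically significant even when the primary has missed. SGIS is the only named secondary efficacy endpoint and matches the only secondary objective. It is the subject's own rating, whereas the primary combines a clinician's CGIC with the modified Ashworth score. A trial that misses on the primary and is positive on SGIS is therefore a realistic outcome, and the readable plan does not say how it would be interpreted. If SGIS were then presented as evidence of efficacy, the error rate across the two endpoints together would exceed 5%.

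**Working it through.** **The plan's own figure.** The readable text gives no error rate for the two endpoints together, so there is nothing to reproduce. The only stated error figure is 5% two-sided per test.

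**Inputs from the documents.** Primary test at two-sided 0.05 (SAP 6.2.1.5). SGIS at two-sided 0.05, inferred from the default in SAP 5.2. No adjustment (SAP 5.2). No interim analysis (SAP 5.4).

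**Assumptions, not in the documents.** The two test statistics are bivariate normal with correlation r between 0 and 0.9. Both null hypotheses are true. SGIS is read as significant whatever the primary shows.

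**Formulas.** Let B be the probability that both |Z1| and |Z2| exceed 1.96.

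- At least one false claim = 0.05 + 0.05 − B
- SGIS falsely significant while the primary is not = 0.05 − B

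For r = 0, B = 0.05 × 0.05 = 0.0025, so the results are 0.10 − 0.0025 = 0.0975 and 0.05 − 0.0025 = 0.0475. For other r, B comes from the bivariate normal distribution.

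| r (assumed) | B | At least one false claim | SGIS alone falsely significant |
|---|---|---|---|
| 0 | 0.0025 | 0.0975 | 0.0475 |
| 0.3 | 0.0049 | 0.0951 | 0.0451 |
| 0.5 | 0.0093 | 0.0907 | 0.0407 |
| 0.7 | 0.0165 | 0.0835 | 0.0335 |
| 0.9 | 0.0296 | 0.0704 | 0.0204 |

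The third column includes the 5% that belongs to the primary under any plan. The last column is the part that an order would remove. At r = 0.7 the unrounded values are 0.08345 and 0.03345, hence 8.3% and 3.3% in the text.

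**With the order primary, then SGIS.** If the primary null is true, any false claim requires the primary to be rejected first, which happens with probability 0.05. If the primary effect is real and the SGIS null is true, the only possible error is on SGIS, at most 0.05. The two-endpoint error is therefore at most 0.05 in every case, and SGIS cannot be falsely claimed after a failed primary.

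**What SGIS gives up.** Its chance of a claim falls from its own power to the probability that both tests are significant. With powers assumed for illustration:

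| Primary power | SGIS power, no order | Ordered, r = 0 | Ordered, r = 0.5 | Ordered, r = 0.7 |
|---|---|---|---|---|
| 0.80 | 0.80 | 0.80 × 0.80 = 0.64 | 0.69 | 0.71 |
| 0.90 | 0.80 | 0.90 × 0.80 = 0.72 | 0.75 | 0.77 |

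**The case against.** The strongest reply is that the documents may already contain the order. SAP 6.2.2.2 is where a condition on SGIS would most naturally stand, and nearly all of it is unreadable; so is the protocol text between 10.4.3.2.1 and 10.4.3.4.2. Nor does SAP 5.2 exclude an order: its 5% default gives way to statements elsewhere, and a fixed sequence leaves p-values unadjusted, so the two could stand together. A reader might infer from 5.2 that the plan has no testing order at all; the documents do not support that. This objection stands, and it limits the point to the readable text.

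A second reply is that nothing readable gives SGIS a confirmatory role. There is one primary null hypothesis (SAP 6.2.1.4), and SGIS sits under the secondary objectives as a corollary measure. This also stands in part: the inflation matters only if SGIS is used to support a claim. But ranking endpoints as primary and secondary is not a testing rule, and the readable plan does not label the SGIS p-value as nominal.

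A reader might also infer that the primary conclusion is compromised. It is not: its type I error is 5% with or without an order.

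Finally, one might think that an ordered test is free. It is free for the primary only; SGIS loses power, as shown above.

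**Conclusion.** The point holds for the readable text: every test has a 5% default, adjustment is ruled out, and nothing makes SGIS depend on the primary. Whether the unreadable text supplies an order cannot be determined from these documents.

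If it does not, and SGIS is read as significant regardless of the primary, the two-endpoint error with both nulls true is 7.0% to 9.8% for assumed correlations of 0.9 down to 0. The chance that SGIS alone is falsely significant is 2.0% to 4.8% over the same range. The correlations are assumptions, but over this whole range the two-endpoint error exceeds 5%. What is at stake is the standing of the only secondary endpoint, not the validity of the primary test.

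**What to change.** State in SAP 5.2 and 6.2.2.2, before unblinding:

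- SGIS is tested at two-sided 0.05 only if the primary analysis is significant at two-sided 0.05; otherwise its p-value is nominal.
- All p-values from additional, exploratory and subgroup analyses are nominal, since the two-step order does not cover them.

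If unreadable text already sets this order, it is enough for 5.2 to refer to it.

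The cost is two sentences. SAP 5.5 already provides for revisiting the planned methods before the blind is broken. Data collection, sample size and the primary analysis do not change. The price is that the sponsor gives up any SGIS claim when the primary fails.
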